### 1. OBJECTIVES

1. **PRIMARY OBJECTIVE:** To assess the effect of absorbable anchor compared to suturing for mesh attachment to vagina in robotic assisted sacrocolopexy on the length of surgery for this portion of the procedure.
2. **SECONDARY OBJECTIVES:**
  - i. To assess intraoperative and
  - ii. postoperative complication rates,
  - iii. Intraoperative 10 cm visual analog scale (VAS), to subjectively assess surgeon satisfaction with the technique
  - iv. post-operative Pelvic Organ Prolapse Quantification (POPQ) evaluation for anatomic failure and
  - v. a VAS of the vaginal walls overall appearance
2. **HYPOTHESES** For women undergoing sacrocolpopexy surgery at a large managed care organization:
  1. **PRIMARY HYPOTHESIS:** Attachment of the mesh to the vagina with absorbable anchors compared to standard treatment (suturing) will require 50% shorter surgical time for the mesh attachment portion of the procedure.
  2. **SECONDARY HYPOTHESIS:** Anchor suture staples compared to standard treatment will:
    - i. have similar rates of intra-operative and post-operative complications
    - ii. have similar rates of surgical failure
    - iii. not have different appearance on the VAS of the vaginal walls
    - iv. elicit higher reported satisfaction from surgeons
3. **BACKGROUND**
  1. **PELVIC ORGAN PROLAPSE:** Pelvic organ prolapse (POP) is the descent of one or more of four different anatomic structures: a) the uterus (cervix), b) the apex of the vagina (in those status post-hysterectomy) c) the anterior vaginal wall, or d) the posterior vaginal wall. It is caused by chronic intra-abdominal pressure on weakened pelvic organ supports. An estimated 41.1% of women aged 50-79 have some degree of prolapse on exam [1,2], while only 2.9-8% of all adult women report symptomatic prolapse symptoms [3-5]. Severity of POP is defined by the Pelvic Organ Prolapse Quantification (POPQ) system [6]. Risk factors include age, childbirth (especially vaginal and operative vaginal deliveries), white race, family history, constipation, obesity, smoking, and menopause. Symptoms can include a vaginal bulge, pressure, or discomfort.
  2. **SACROCOLPOPEXY:** Sacrocolpopexy (SCP) is a common surgical treatment for symptomatic pelvic organ prolapse. While traditionally reserved for women with recurrent or vaginal vault prolapse SCP is becoming more common as the first surgical option for women with prolapse [7], because benefits are long-lasting with less than 5% of patients undergoing reoperation [8-11]. However, SCP is associated with an increased rate of intraoperative and post-operative complications compared to other surgical treatments [12], including bowel obstruction, mesh erosion, and venous thromboembolism. More recently minimally

invasive SCP (laparoscopic and robotic assisted) has become popular as it offers similar success rates with faster recovery, less pain, bleeding and cost [13-15]. Robotic surgery has several unique challenges including the absence of haptic feedback, and additional time required for setup. The mean time to complete robotic SCP is 79 minutes for attendings, and 76 minutes for trainees, with total operating time of 182 minutes for attendings, and 200 minutes for trainees [16].

[figure not shown]
3. **ANCHOR MESH FIXATION:** Anchor mesh fixation has been tested successfully in several applications. In laparoscopic incisional and ventral hernia repair, anchors have been used to fixate mesh. A systematic review [17] found four trials involving 207 surgeries comparing traditional suture mesh fixation to anchoring. Anchoring was associated with shorter operative time, less postoperative pain and similar rates of perioperative complications and hernia recurrence and shorter hospital stay. Both non-absorbable (titanium helical anchors) and absorbable anchors (Absorboanchor™, Covidien; Sucerestrap™, Ethicon) have been used with similar operating time, postoperative hospital stay, pain, morbidity and recurrence [18-21]. However longer term studies have reported more pain and erosion of non-absorbable anchors into hollow viscera [22] but perhaps higher recurrence rates with absorbable anchors[23]. Comparison of acute fixation strength of various attachment techniques has been performed, finding suture to provide the greatest strength and non-absorbable to provide more strength than absorbable anchors [24]. However, it is well known that mesh used for vaginal attachment is incorporated into the tissue after three months and the use of absorbable sutures for mesh attachment for sacrocolpopexy are commonly used [25].
4. **PRIMARY OUTCOME MEASURE:** The primary outcome measure is mesh attachment time to the fibromuscular tissue layer in the vagina. In sacrocolpopexy done in a minimally invasive fashion, polypropylene mesh attachment to this layer of the vagina can be the most technically challenging and time intensive portion of the surgery. This is traditionally performed with non-barbed, delayed absorbable interrupted, suture (such as 2-0 PDS), with 4-6 interrupted sutures with 4 to 6 knots each on both the anterior and posterior aspect of the vagina. The anterior mesh attachment took 15 minutes, while posterior mesh attachment took 16 minutes on average [16] and the time to complete both took 42 minutes in another study[25]. The mesh attachment time has excellent validity as it directly measures the time it takes to complete the part of the surgery. With few exceptions, the measure of time has strong accuracy and precision due to the use of standardized procedures and consistent measurement technique.
5. **RATIONALE AND POTENTIAL SIGNIFICANCE OF RESULTS:** By applying a commonly used surgical technique of absorbable anchors to a new surgery, SCP, operative time may be decreased while providing similar patient outcomes. Absorbable anchors have been validated in mesh fixation during laparoscopic surgical repair of hernias. This

technique potentially takes less time than traditional suturing, thus decreasing cost and morbidity of anesthesia. Our hypothesis proposes that for women undergoing SCP at a large managed care organization, those receiving anchor suture staples to attach the mesh to the vagina compared to those receiving standard treatment will require 50% shorter surgical time for the mesh attachment portion of the surgery. Our secondary hypothesis is for women undergoing SCP at a large managed care organization, those receiving anchor suture staples to attach the mesh to the vagina compared to those receiving standard treatment will have similar rates of intra-operative and post-operative complications and surgical failure. On VAS, patients will not have different appearance of the vaginal walls. Surgeons will report higher satisfaction with the anchor technique.

#### **4. OVERVIEW OF DESIGN**

1. **DESIGN DESCRIPTION;** This is a multi-site prospective, randomized, single-blind, 2 arms-parallel, clinical trial to evaluate the effect of absorbable anchor versus suturing of polypropylene mesh to the vaginas fibromuscular layer on the length of procedure for women undergoing SCP for POP. This effect will be studied using timing of the surgical procedure.
2. The study consists of a 1-year enrollment period concurrent with a 1-year single blinded period (the intraoperative data in which the patient is blinded to group assignment, but the surgeon/investigator is not), followed by a 6-month postoperative double blinded period (in which both the patient and surgeon/investigator).
3. During enrollment, patients who meet the inclusion and not the exclusion criteria and provide informed consent for participation will be assigned randomly to receive either absorbable anchor mesh fixation or suture mesh fixation.

Figure 1. Flowchart of study schema

4. **SCREENING PERIOD:** Subject will be screened for eligibility during a 1-year period that will include the preoperative office visit and preoperative unit visit. Office staff (research nurses, nurse practitioners, residents, fellows, attendings) will obtain written informed consent from participants as a part of enrollment. Standard physical exam measures (including POPQ) will be performed during the office visit. The suture allocation sealed envelope will be opened intra-operatively once it is certain the attachment of mesh will occur via a technique that is minimally invasive.
5. **STUDY PERIOD:** Study duration will be the 1 year concurrent period where surgeries are performed as well as the subsequent 6 months where postoperative visits occur. After randomization and surgery occurs subjects will follow up for a total of 6 months, with three visits, one at 6 weeks, one at 6 months. During these postoperative visits, a standard physical exam will be performed looking for signs of POP recurrence, mesh erosion, palpable suture, anchors, and other physical findings. The

patient will complete standardized questionnaires assessing pain, satisfaction and other quality of life indicators.

6. **STUDY POPULATION:** Women with POP, scheduled for minimally invasive SCP will be eligible for enrollment

i. **INCLUSION CRITERIA:** All patients must meet all the following inclusion criteria.

1. Age 21 or older
2. Diagnosis of POP, defined as the descent of one or more of four different anatomic structures, a)the uterus(cervix), b)the apex of the vagina (in those status post hysterectomy) c) the anterior vaginal wall, or d) the posterior vaginal wall. This is defined on exam as the POPQ points Ba, C, or Bp >0 cm beyond the hymen, uterine(cervix) descent into at least the lower half the vagina (defined as point c> -tv/2) or post hysterectomy vault into the lower 2/3 of the vagina.  
Bothersome bulge symptoms as indicated on question 3 of the Pelvic Floor Disorder Inventory (PFDI-20) form relating to 'sensation of bulging' or something 'falling out'
3. Desire surgical treatment for POP with SCP
4. Available for up to 6 months of follow up
5. Not pregnant or desiring future pregnancy
6. Written informed consent is obtained.

ii. **EXCLUSION CRITERIA;** Patients are ineligible for the study if:

1. Known adverse reaction to synthetic mesh, or complications including but not limited to erosion, fistula, or abscess.
2. Cervical intraepithelial neoplasia (CIN2, CIN3, or cancer)
3. Unresolved chronic pelvic pain
4. Prior abdominal or pelvic radiation
5. Contraindications to the surgical procedures including known horseshoe kidney, pelvic abscess or active diverticular abscess or diverticulitis

7. **METHODS OF RECRUITMENT AND MULTIPLE STRATEGY OF RETENTION:** There are many women in the target population. We will educate the health personnel (research nurses, nurse practitioners residents, fellows, attendings) in two sites of a large managed care organization Female Pelvic Medicine and Reconstructive Surgery (FPMRS) to recruit this population. Subject retention strategies will include a \$20 visa gift card given to the subject on completing the 6 month follow up appointment, as well as phone call reminders of those appointment.

5. **STUDY PROCEDURES**

1. **INTERVENTION:** On day of surgery eligible individuals are randomized to have either absorbable anchor or suture fixation of mesh (Figure 1). The patients and all postoperative study staff will be blinded to treatment assignment and surgical time measurements. A block stratification with a computer-generated randomization schedule will be performed.  
Equipment needed for both techniques will be stocked and readily

available and all surgeons will be trained in the use of both techniques. The two groups will be mesh attachment with 0 non-barbed delayed absorbable suture or anchor suture using the Reliatack™ articulating reloadable fixation device (Medtronic). A minimum number of suture attachment points will be 4 on each side of the vagina. The average number for most cases is typically 6 to 8 per side. The same number minimum number of anchors will be required for the anchor arm. The remaining portion of the procedures will be the same for both arms. Intra-operative details will be tracked including number of sutures/anchors placed per side, inability to complete anchor placement or suture placement and alternative method if needed, and anchor or suture exposure full thickness in the vagina, and insertion of anchor/suture in rectum or bladder requiring removal. The type of suture will not be revealed in the operative procedure or heading but will be described in the description of procedure. Perioperative antibiotics will be administered per operating room protocol. Patients will all be prescribed vaginal estrogen after surgery.

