## 6. DATA MANAGEMENT AND ANALYSIS

1. PROCEDURES FOR DATA COLLECTION: Study participants will be closely observed by investigators to make sure that surgical appointments are set up. Data from preoperative period will be taken from the the EMR for the subject. Data for the primary outcome will be abstracted when the subject has their surgery.  
A Clinical report Form (CRF) will be used to collect history, physical examination, operation, operating times, technique, mesh attachment interval times, complications, and subsequent follow-up examination data. The investigators will input data into a pre-formatted spreadsheet. The spreadsheet will be maintained through the Kaiser Permanente San Diego research department on a password protected server and will be audited, reviewed and maintained by the investigators
  - i. Quality of Data: Data of the highest quality will be obtained from management data defined protocols for evaluating its accuracy (using source verification), completeness, accountability, and integrity.
  - ii. Completeness: the investigators will identify and complete any missing data.
  - iii. Accuracy: Errors in data will likely stem from errors in data entry. To minimize this, confirmation of data with a second source and random checks of data, and will be done. Error catching mechanisms in the Excel spread sheet and Access Database will be created with appropriate ranges and limits to help catch mistakes in data entry and allow for more accurate data entry.
  - iv. Auditing: Both sample and schedule-based auditing will be performed. Quarterly audits will be performed with random selection of 10% of the data to verify. Administrative audits will be done on a similar schedule to ensure compliance with Good Clinical Practices of the FDA.
  - v. Accountability: Accountability for data entry and data management will be with the investigators and statistical consultants.
  - vi. Integrity: mirrored hard drives, data back ups and storage on Kaiser Permanente San Diego server, will insure for data integrity.
2. ANALYSIS OF BASELINE DATA: Subject characteristics (measures and demographic information) collected at baseline will be compared across treatment groups, using either chi-square for categorical variables or t-test for continuous variables. We will examine these baseline characteristics for statistically significant differences between treatment groups, and use those that are identified for adjusted analysis correcting for these

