differences in analysis of outcome variables.

3. **STATISTICAL ANALYSIS OF OUTCOMES:** The primary endpoint for this study is the time of completion of mesh attachment. Statistical methods will include t-test or Mann Whitney U test for continuous variables, and chi-squared or Fischer's exact-test for categorical variables. We will collect the primary measure for outcomes of time of mesh attachment as a continuous variable. In addition we will use t-tests to evaluate the mean times of the different attachment approaches. Paired sample t test will be used to evaluate POP-Q values pre and postoperatively. Chi-squared test will be used to examine anatomic failures between the two. We will do risk analysis as appropriate using 95% confidence intervals odds ratios. For the analysis we will use SPSS 22.0.
4. **STUDY POWER AND SAMPLE SIZE:** A time of mesh attachment power calculation was performed using Power and Sample Size program (PS version 3.1.2). If suture mesh attachment interval =  $40 \pm 20$  mins [16,25], a 50% reduction with use of anchors is =  $20\text{mins} \pm 20$  mins. With 80% power and  $\alpha=0.05$ , 17 subjects will be needed for each arm. Anticipating a drop out of up to a 30% we will enroll 25 subjects in each group for a goal of at least 17 participants for each arm.

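### Randomisation is by stratified blocks with no factor named, and attachment time is compared without the stratum; if the stratum predicts time, the primary test is conservative

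*Protocol*

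**What the plan says.** **Allocation.** Protocol 5.1 (Intervention): "A block stratification with a computer-generated randomization schedule will be performed". Neither document gives the stratification factor or the block size. Section 4.7 places recruitment "in two sites of a large managed care organization Female Pelvic Medicine and Reconstructive Surgery (FPMRS) to recruit this population", but site is not called a stratum there or elsewhere. Section 5.1 adds that "all surgeons will be trained in the use of both techniques", so there is more than one operator. Their number is not given, and operator is not called a stratum either.

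**Analysis.** Protocol 6.3 and SAP 1.3 carry the same text. "The primary endpoint for this study is the time of completion of mesh attachment". Methods "will include t-test or Mann Whitney U test for continuous variables", followed by: "In addition we will use t-tests to evaluate the mean times of the different attachment approaches". No term for stratum, site or operator appears.

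**Adjustment.** Protocol 6.2 and SAP 1.2 test baseline subject characteristics for differences between arms and "use those that are identified for adjusted analysis correcting for these" differences. This is the only adjustment planned.

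**The concern.** Stratified blocks hold the arms in near-equal numbers within each stratum, so differences between strata largely cancel out of the arm comparison. A plain two-sample test does not know this and leaves the between-stratum variation in its error term. If the stratum is related to attachment time, the reported standard error exceeds the true variability of the estimate. Confidence intervals are then too wide, and the test rejects a true null less often than 5%.

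The adjustment rule is unlikely to repair this. It acts only on characteristics that differ significantly between arms, and a factor balanced by the randomisation will seldom do so, however strongly it predicts time.

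At stake is precision in the primary comparison that the randomisation has already bought. Because the factor is not named, a reader also cannot tell which term the analysis should carry.

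**Working it through.** **1. Inputs.** From Protocol 6.4 and SAP 1.4: means 40 and 20 min, SD 20 in both arms, alpha 0.05, 80% power, 17 evaluable and 25 enrolled per arm. Assumed, because the documents are silent: two-sided alpha, two balanced strata, normal errors, additive stratum effects, total SD held at 20. The share of variance due to the stratum, R², is not given, so 0% to 40% is shown.

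**2. The plan's own figure.** The exact two-sample t-test with a 20-min difference and SD 20 has power 0.781 at 16 per arm and 0.807 at 17. So 17 is reproduced. Allowing for 30% dropout, 17/0.70 = 24.3, which rounds up to the planned 25.

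**3. Size of the standard-error mismatch.** Plain standard error at 17 per arm: 20 × √(2/17) = 6.86 min. True standard error under balance: 6.86 × √(1 − R²). Their ratio is 1/√(1 − R²).

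| R² | Plain SE (min) | True SE (min) | Ratio |
|---|---|---|---|
| 0% | 6.86 | 6.86 | 1.000 |
| 10% | 6.86 | 6.51 | 1.054 |
| 20% | 6.86 | 6.14 | 1.118 |
| 40% | 6.86 | 5.31 | 1.291 |

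**4. Effect on the test.** Simulation with 34 evaluable patients under the assumptions in step 1:

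| R² | Type I error, plain t-test | Power, plain | Power, stratum in model |
|---|---|---|---|
| 0% | 0.050 | 0.80 | 0.80 |
| 10% | 0.040 | 0.81 | 0.84 |
| 20% | 0.027 | 0.83 | 0.88 |
| 40% | 0.010 | 0.86 | 0.95 |

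The adjusted model stays at about 0.05 throughout. A separate simulation with permuted blocks of 4 gave the same pattern at R² of 10%, 30% and 50%: type I error 0.041, 0.023 and 0.006 for the t-test, and 0.036, 0.023 and 0.005 for Mann-Whitney. Switching to the rank test therefore does not help.

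**5. Which R² is plausible?** With two equal strata a gap of g minutes gives R² = (g/2)²/20², so g = 40 × √R². The gap is 12.6 min for 10%, 17.9 for 20% and 25.3 for 40%. The last exceeds the whole 20-min treatment effect. The documents allow two rough comparisons:

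- Protocol 3.4 cites mean attachment times of 15 + 16 = 31 min in one study and 42 min in another. If two strata differed by that 11 min, R² = 5.5²/20² = 7.6%, and the standard error would be about 4% too large.
- Protocol 3.2: "The mean time to complete robotic SCP is 79 minutes for attendings, and 76 minutes for trainees". A 3-min gap gives R² = 1.5²/20² = 0.6%. This is sacrocolpopexy time, not attachment time. Total operating time in the same sentence differs more (182 against 200 min).

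**6. Operator.** With six operators explaining 30% of the variance and allocation not stratified by operator, the plain t-test is valid: type I error 0.043, and mean standard error 6.8 against an actual SD of the estimate of 6.8. Adding operator only raises power, from 0.79 to 0.87.

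**The case against.** Four objections deserve weight.

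- **The stratum is unknown.** A reader might infer that site and operator are the strata, and so that leaving both out makes the error bars wrong. The documents do not support this: site appears under recruitment and operators under training, and neither is tied to the allocation schedule. For an operator factor that was not stratified, omission costs efficiency only (step 6). This objection stands and limits the point to the stratum itself. The wording in section 5.1 could even mean blocking alone; if so, there is no mismatch of this kind.
- **The gain is smaller than it first looks.** One might set the planned power of 0.807 against 0.846, 0.885 and 0.954 (residual SD reduced by 10%, 20% and 40% of variance) and claim gains of about 4, 8 and 15 points. But the plain test's power also rises under balanced strata, because the estimate varies less. The real gains are about 3, 5 and 10 points. This stands.
- **The direction is safe.** Intervals are too wide rather than too narrow, and type I error is below 5%. This stands.
- **Operator data may be available anyway.** The intra-operative lists do not name operator identity, but they do not claim to be complete. Section 5.2.vi also requires that the postoperative examiner is not the operating provider, so the operator must be known. A claim that the information will be lost would go too far.

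What remains is that a stratified allocation is specified without its factor, and the planned analysis ignores it.

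**Conclusion.** The point holds in limited form, as a low-cost improvement. The documents specify stratified randomisation, do not say by what, and plan a primary comparison without the stratum. If the stratum predicts attachment time, the plain standard error is 5%, 12% or 29% too large at R² of 10%, 20% or 40%, and the test is conservative to the extent shown in step 4. If the stratum has no effect on time, nothing is lost. These sizes rest on two balanced strata, SD 20 and an assumed variance share; the figures in step 5 favour the low end.

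A reader might infer that the trial is underpowered or that a significant result would be suspect. Neither follows: unadjusted power stays at about 0.80 or more across the range, 17 per arm remains sufficient, and the error works against a positive finding.

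**What to change.** 1. In Protocol 5.1, state the stratification factor or factors actually used, and the block size. If allocation was blocked but not stratified, say so; the change in item 2 is then not needed.
2. In Protocol 6.3 and SAP 1.3, replace the unstratified t-test or Mann-Whitney with a linear model of attachment time on arm plus those factors as the primary comparison. Name a stratified rank test (van Elteren) as the alternative if times are skewed, which an anchor-arm assumption of 20 ± 20 min makes possible.
3. Optional: record an operator code and role at surgery and use them as a covariate. This gains efficiency. It corrects the error bars only if allocation is also stratified by operator.

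The cost is wording, plus one data field if item 3 is taken up, and about one degree of freedom per extra stratum: 32 falls to 31 with two strata at 17 per arm. With six strata and no stratum effect at all, simulated power moved from 0.80 to 0.78, so the factors should be kept few.
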